8.5 Risks and/or Benefits to Patients

ESRD patients are often ill, and are prone to a variety of adverse events on or off HD, ranging, for example, from infections to hypertension to bleeding to thromboembolism to acute ischemic cardiovascular emergencies, even if they are apparently stable on chronic HD. A temporal and modest increase in blood pressure was observed in one study subject in the FIH study after xisomab 3G3 administration, and the event was deemed potentially related to the study drug.

Xisomab 3G3 is a purified protein produced by recombinant DNA technology in a mammalian cell culture system, and these types of drugs can, occasionally and unpredictably evoke acute allergic reactions. Some ESRD patients develop chronic HD- and uremia-related moderate hemorrhagic diathesis or hemostasis impairment. Even though currently available data do not indicate a hemostatic function for the FXI/FXII interaction, there remains a theoretical possibility of contact activation-mediated enhancement of hemostasis. Thus, the hemostatic safety of xisomab 3G3 in the complex conditions of ESRD and chronic HD is not yet known. The safety monitoring practices employed by this protocol (i.e., 12-lead ECG, vital signs, blood pressure, clinical laboratory tests, AE questioning, vascular access site (AV fistula or AV graft) monitoring, and physical examination) are adequate to protect the patients' safety and should detect all expected and unexpected treatment-emergent AEs (TEAEs). In addition, the cohorts will be dosed in a sequential manner, starting with the lower dose level, Cohort 1.

Patients undergoing heparin-free HD may be at higher risk of developing clots within the hemodialyzer. Should this occur, site standard operating procedures will be followed to replace the clotted dialyzer and resume HD under the supervision of the PI. It is important to note that replacement of the dialyzer cartridge is a safe procedure for the patient. While studies suggest that there is no risk of thromboembolic complications should this occur, clotting of the dialyzer circuit could result in up to ~228 mL of blood loss.

There may be direct health benefit for study participants from receipt of study drug, some evaluated among the secondary outcome measures. Xisomab 3G3 and its murine precursor, 14E11, have shown anti-inflammatory and antithrombotic effects in non-clinical studies. Both inflammatory responses to exposure of blood to the foreign surfaces of the HD equipment, and thrombus formation-related consumption of blood components, anywhere in the body, or thrombus layer entrapment in the dialyzer equipment, especially in the absence of systemic anticoagulation with heparins, may be reduced in the presence of pharmacologically active levels of xisomab 3G3. Reduced thrombus accumulation on the dialyzer surface may potentially improve the efficiency of hemodialysis as well. An indirect health benefit for study participants enrolled in this study is the free medical tests received at screening and during the study.

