| | attempt will also be made to approximately match key characteristics, including sex, average age, and weight per cohort. |
| Dosage, Dosage Form, Route, and Dose Regimen: | 
On Day 1, patients in each cohort will receive a single dose of xisomab 3G3 or placebo injection into the proximal (arterial) dialysis line on one occasion. Cohort 1 will be conducted prior to initiation of Cohort 2.
 
Planned doses will be as follows:
 
Cohort 1: 0.25 mg/kg xisomab 3G3 or matching placebo
 
Cohort 2: 0.5 mg/kg xisomab 3G3 or matching placebo
 |
| Key Assessments: | 
Safety
 
Safety assessment will include physical examinations, vital signs, ECGs, clinical laboratory tests, vascular access site reaction, bleeding time, and AEs.
 
Number/severity of AE will be tabulated and summary statistics for the 12-lead ECGs, vital signs, and clinical laboratory tests may be computed and provided, as deemed clinically appropriate.
 
Pharmacodynamics:
 
Efficacy/potency assessment will be measured as efficiency of the hemodialysis by assessing thrombus accumulation (ranked by visual inspection) in the dialyzer cartridge, protein accumulation in the HD filter, BUN and potassium blood levels, length of HD, measurement of urea removed by 3 hours of dialysis, and total dialysate urea (Kt/V and urea reduction ratio [URR]). Coagulation tests will also be performed.
 
Change from baseline will be summarized by treatment (2 active dose levels and pooled placebo) and per timepoints using descriptive statistics.
 
Pharmacokinetics:
 
The following PK parameters will be calculated for xisomab 3G3 in plasma, as appropriate: AUC_{0-t}, AUC_{0-inf}, AUC%extrap, C_{max}, T_{max}, K_{el}, t_{1/2}, CL, and V_{ss}.
 
PK parameters will be summarized by dose level using descriptive statistics.
 
Immunogenicity:
 
Development of antibodies against the study drug will be evaluated by determining the anti-drug antibody (ADA) titer.
 |

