8.4.2 Rationale for the Dose Selection

Doses of 0.25 mg/kg and 0.5 mg/kg were selected for this phase 2 study in order to provide adequate PD and PK characterization but still allowing a safety margin should the results differ in this population compared to healthy subjects. The 0.25 mg/kg xisomab 3G3 dose is 2.5-fold higher than the lowest dose in the FIH study. The 0.1 mg/kg dose in the FIH study had a short and modest, yet detectable PD effect (several seconds of temporal aPTT prolongation). The 0.25 mg/kg dose is expected to provide an initial plasma concentration that is within the range of average FXI concentration, the molecular target of xisomab 3G3, in human subjects, and may approach saturation in some individuals after full distribution. Therefore, it has the potential to exert brief pharmacological (anti-inflammatory, antithrombotic) activity, possibly lasting up to a day, until elimination of the antibody and hepatic FXI secretion that neutralizes the antibody.

The 0.5 mg/kg dose was safely administered in the FIH study and allowed adequate characterization of the PK profile in healthy adults. In addition, following a 0.5 mg/kg a prolongation of aPTT was seen, with highest values measured at 24 hours postdose and having a sustained effect for at least 72 hours postdose. The 0.5 mg/kg xisomab 3G3 dose is expected to provide, after complete distribution, a plasma concentration that is approximately twice the average human plasma concentration of the FXI antigen. Therefore, this dose is expected to be overcome by FXI generation later, and have pharmacological activity that lasts longer than the lower dose level.

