12.3 Method of Assigning Patients to Treatment Groups

Each patient will be assigned a unique identification number upon screening. Patients who complete the study screening assessments and meet all the eligibility criteria will be assigned a unique randomization identification number at the time of dosing, different from the screening number, and will receive the corresponding product, according to a randomization scheme generated at Celerion.

Patients will be enrolled to Cohort 1 or Cohort 2 with Cohort 1 conducted prior initiation of Cohort 2. In each cohort, an attempt will be made to enroll at least 50% of females and at least 30% of a race/ethnicity minority group. An attempt will also be made to approximately match key characteristics, including sex, average age, and weight per cohort.

In each cohort, patients will be randomized to receive either xisomab 3G3 or placebo maintaining a 2:1 ratio

If replacement patients are used, the replacement patient number will be 100 more than the original (e.g., Patient No. 101 will replace Patient No. 1).

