13.2.6 Bleeding of Access Site

Evaluation of bleeding and bleeding time from the HD vascular access sites on the AV fistula or AV graft using the ladder or buttonhole technique will be performed as per Study Events Flow Chart ([Section 6](#)).

Following hemodialysis, the needle will be removed from the vascular access site and immediately followed by the placement of the dressing (i.e., gauze). Pressure will be applied manually by a clinical associate for 10 minutes before checking for evidence of bleeding around the dressing. If there is still some bleeding, pressure will be applied back at the site for 5 minutes. The site will then be checked again for evidence of bleeding; this procedure will be repeated every 5 minutes until bleeding has stopped. Once bleeding has stopped, a new gauze dressing is applied and then taped. To ensure consistency when applying the pressure, the clinical staff will have received adequate training and an attempt will be made to have the same associates perform this test.

The time to clot will be recorded.

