13.2.8.2 Monitoring

Patients will be monitored for AEs from check-in through completion of the study. Patients will be asked how they are feeling once per day during confinement and at each return/follow-up visit.

AEs (whether serious or non-serious) and clinically significant abnormal laboratory test value(s) will be evaluated by the PI or designee and treated and/or followed up until the symptoms or value(s) return to normal, or acceptable levels, as judged by the PI or designee.

Treatment of serious adverse events (SAEs) will be performed by a licensed medical provider, either at the CRU or at a nearby hospital emergency room. Where appropriate, medical test(s) and/or examination(s) will be performed to document resolution of event(s). Outcome may be classified as resolved, improved, unchanged, worse, fatal, or unknown (lost to follow-up).

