### 4.2 Preliminary Data and Interim Analysis

Celerion has not been contracted to complete any interim safety, PK, and PD analyses.

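### Cohorts are dosed low dose first, but nothing requires Cohort 1 to be reviewed as a group, or a decision recorded, before Cohort 2 receives 0.5 mg/kg

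*Protocol*

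**What the plan says.** Section 8.5 of the protocol states that "the hemostatic safety of xisomab 3G3 in the complex conditions of ESRD and chronic HD is not yet known". It then judges the planned monitoring adequate and adds: "In addition, the cohorts will be dosed in a sequential manner, starting with the lower dose level, Cohort 1".

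Every other statement about the cohort step also gives order only. The Synopsis has "Cohort 1 will be conducted prior to initiation of Cohort 2". Section 12.3 has "Patients will be enrolled to Cohort 1 or Cohort 2 with Cohort 1 conducted prior initiation of Cohort 2". Protocol Section 10.1 and SAP Section 3 say that dosing is sequential and no more. None of them names a reviewer, the data to be seen, a minimum follow-up, a criterion for going on, or a record of the decision.

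SAP Section 4.2 reads: "Celerion has not been contracted to complete any interim safety, PK, and PD analyses". Under protocol Section 12.4.3 the randomization stays closed until database lock unless there is a medical emergency, so the planned by-treatment summaries come after Cohort 2 has been dosed.

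The protocol does contain safety review. Section 13.2.8.2 provides that "AEs (whether serious or non-serious) and clinically significant abnormal laboratory test value(s) will be evaluated by the PI or designee". Section 13.2.8.3 has the PI or designee assess each AE for causality and severity. Section 13.2.8.4 sends SAEs to the sponsor within one working day. Section 12.4.2 lets the blind be broken for a whole dose level in an emergency that appears to threaten other patients. Section 15.2 lets the sponsor halt or end the study at any time.

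**The concern.** Giving the lower dose first protects later patients to the extent that someone uses what the lower dose showed. Here each safeguard works on one patient or one event, needs an emergency, or is left to discretion. None is tied to the move from 0.25 to 0.5 mg/kg.

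The gap matters most for bleeding. Bleeding time belongs to the primary safety outcome (Section 9.2). Section 13.2.6 has the time to clot recorded, but no section gives a length at which it must be reported as an AE, and Section 13.2.8.1 excludes aPTT prolongation from AEs. A moderate lengthening in several Cohort 1 patients could therefore pass each individual check and become visible only when the readings are put side by side.

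The step is 2-fold in dose, but Section 8.4.2 expects a longer effect. At 0.25 mg/kg it expects "brief pharmacological (anti-inflammatory, antithrombotic) activity, possibly lasting up to a day". At 0.5 mg/kg in healthy subjects the aPTT effect lasted at least 72 hours, long enough to cover the Day 3 dialysis session at 48 hours as well as Day 1.

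**Working it through.** The plan has no figure to reproduce: Section 14.1 says that the sample size has no statistical basis. The check is a comparison of the text (above) plus arithmetic on what a group review could and could not show.

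**Who is affected.** With 9 to 12 patients per cohort at 2:1, active patients number (2/3) × 9 = 6 to (2/3) × 12 = 8, and placebo patients 3 to 4, in each cohort.

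**What a Day 6 review would contain.** Bleeding time is scheduled on Days -7, -5, -3, 1, 3 and 5 by then.
- All readings: 6 × 9 = 54 to 6 × 12 = 72.
- Post-dose readings on active drug: 3 × 6 = 18 to 3 × 8 = 24.
- Day 1 readings on active drug: 6 to 8. Only these fall clearly within the duration of effect expected at 0.25 mg/kg.

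**Chance that a harm appears in Cohort 1.** For n = 6 or 8 active patients and true rate p, P(at least one) = 1 − (1 − p)^n and P(at least two) = 1 − (1 − p)^n − np(1 − p)^(n−1). The rates are assumptions, because the documents give none.

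| Assumed rate | At least one (n = 6 to 8) | At least two (n = 6 to 8) |
|---|---|---|
| 5% | 26–34% | 3–6% |
| 10% | 47–57% | 11–19% |
| 20% | 74–83% | 34–50% |
| 30% | 88–94% | 58–74% |

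These are chances that events occur, not that a blinded reviewer attributes them to the drug. If no events occur, the one-sided 95% upper bound is 1 − 0.05^(1/6) = 39% or 1 − 0.05^(1/8) = 31%.

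**What the bleeding measure can show.** Section 13.2.6: "Pressure will be applied manually by a clinical associate for 10 minutes before checking for evidence of bleeding around the dressing". After that the site is rechecked every 5 minutes. Lengthening that stays below 10 minutes is invisible, and above that the scale is coarse. The documents give no SD for bleeding time, so I state no detectable shift in minutes.

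**Reassurance from healthy subjects.** Sections 8.3 and 8.3.1 report no SAEs, with 4 active subjects at each dose. Pooling 0.5, 2 and 5 mg/kg gives 0 of 12 and an upper bound of 1 − 0.05^(1/12) = 22%. At 0.5 mg/kg alone, 0 of 4 gives 1 − 0.05^(1/4) = 53%. None of these subjects had ESRD. On exposure, Table 1 gives mean AUC0-inf at 5 against 0.5 mg/kg of 28,290,000 / 370,400 = 76 times, and Cmax of 127,300 / 11,250 = 11 times.

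**The case against.** The strongest reply is that Cohort 1 is already observed closely. Patients are confined from Day -8 to Day 6 and asked daily how they feel. A physician assesses every AE, SAEs reach the sponsor quickly, and the sponsor can suspend without giving a reason. SAP Section 4.2 says only what the CRO was contracted to do; it does not bar the PI or sponsor from looking. Section 8.4.2 says that the doses leave a safety margin in case this population behaves differently, and exposures far above those at 0.5 mg/kg have been given to healthy subjects. A blinded review of 9 to 12 patients is also insensitive, and Cohort 1 says little about the longer effect expected in Cohort 2.

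Most of this stands, and it sets the size of the point. A reader might infer that the trial has no safety oversight, that Cohort 1 data would go unseen, or that 0.5 mg/kg is an untested dose. The documents support none of these. A reader might also infer that a group review would reliably catch a bleeding effect, and the arithmetic above does not support that.

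What remains is narrower. The margin was measured in healthy subjects, whereas Section 8.5 calls hemostatic safety in ESRD unknown. The individual checks do not put bleeding times together. No one has to decide, on the record, that the dose may be doubled.

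**Conclusion.** The point holds in a limited form. The plan cites low-dose-first dosing as an added protection but does not require the group review and recorded decision that would link Cohort 1's results to Cohort 2. Six to eight patients are affected. The benefit of adding the step is real but modest: it could reveal common harms or large bleeding shifts before the dose is doubled, and it would usually miss rarer or smaller ones. It is worth making because it is cheap and bears on patient safety. It does not mean that the planned analysis is wrong or that the dose is unsafe.

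The conclusion rests on the protocol and SAP alone. The event rates are assumed. The dosing manual and the site and CRO procedures were not available. If one of them already requires such a review, citing it in Section 10.1 would settle the point.

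**What to change.** Add a paragraph to protocol Section 10.1, cross-referenced in 8.5 and 12.3, stating that no Cohort 2 patient is dosed until both conditions are met:

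1. All dosed Cohort 1 patients have reached Day 6 or terminated early.
2. The PI and medical monitor have documented a blinded review, with a recorded decision to proceed, pause or stop.

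The review covers AEs and SAEs, access-site bleeding times (pre-dose sessions against Day 1 first, then Days 3 and 5), hemoglobin, platelets and dialyzer clotting. Day 12 data are added where available. Hemoglobin needs care, because blood sampling and any clotted circuit lower it in both arms.

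The sponsor's clinicians should set simple pause triggers in advance, such as any related SAE or a stated number of patients with markedly prolonged access-site bleeding. Without a follow-up cut-off and triggers, a recorded meeting would add little to the existing event-by-event review. If the CRO prepares the listings, SAP Section 4.2 should refer to the review.

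The cost is one paragraph, listings of data already scheduled, and a short meeting of existing roles (the medical monitor already appears in exclusion criterion 9). No unblinding or extra patients are needed. A brief pause between cohorts is possible. If Cohort 1 being conducted first means that its Day 12 visits are complete, the Day 6 condition adds no waiting of its own; the protocol does not say.

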9 OBJECTIVES AND ENDPOINTS

9.1 Objectives

The primary objective of this study is:

- To assess the safety and tolerability of a single dose of xisomab 3G3 when injected through a port into the proximal (arterial) dialysis line immediately after initiation of a HD procedure in patients with ESRD.

The secondary objectives of this study are:

- To assess the PD of a single dose of xisomab 3G3 when injected through a port into the proximal (arterial) dialysis line immediately after initiation of a HD procedure in patients with ESRD.
- To assess the efficacy of a single dose of xisomab 3G3 on HD efficiency when injected through a port into the proximal (arterial) dialysis line immediately after initiation of a HD procedure in patients with ESRD.
- To assess the PK of a single dose of xisomab 3G3 when injected through a port into the proximal (arterial) dialysis line immediately after initiation of a HD procedure in patients with ESRD.

9.2 Endpoints

Primary outcome measures:

- The safety and tolerability of xisomab 3G3 will be evaluated versus pre-treatment and placebo by reviewing number and severity of adverse events and use of concomitant medications, physical examination, vascular access site reaction, bleeding time, and changes in vital signs, ECGs, and clinical laboratory evaluations.

Secondary outcome measures:

- PD using dose-dependency of drug potency, determined by measuring changes in coagulation parameters, and thrombus accumulation (assessed and ranked by visual inspection) within the dialyzer cartridges and total protein accumulation in the HD filter after xisomab 3G3-treatment versus pre-treatment and placebo.
- Efficacy on hemodialysis efficiency using BUN and potassium levels before and after hemodialysis, length of HD, measurement of urea removed by 3 hours of dialysis, and total dialysate urea (single pool Kt/V and URR) after xisomab 3G3-treatment versus pre-treatment and placebo.

Other outcome measures:

- PK parameters of xisomab 3G3, calculated, as appropriate: AUC0-t, AUC0-inf, AUC%extrap, Cmax, Tmax, Kel, t^{1/2}, CL, and Vss.
- Development of immunity or antibodies against xisomab 3G3 after drug exposure.

10 STUDY DESIGN

10.1 Overall Study Design and Plan

This is a phase 2, randomized, double-blind, placebo-controlled, single-dose study of xisomab 3G3 designed to evaluate the safety, efficacy/potency, and PK at 2 dose levels administered to patients with ESRD undergoing HD.

A total of up to 24 adult male and female patients will be enrolled; 9-12 patients are planned for each cohort. In each cohort, an attempt will be made to enroll at least 50% of females and at least 30% of a race/ethnicity minority group. Patients will be enrolled into Cohort 1 or Cohort 2; cohorts will be dosed sequentially. Within a cohort, patients will be randomized to active drug or placebo as summarized below:

Table 2: Cohort and Treatment Randomization

| Cohort | Treatment | Active:Placebo | Cohort Size |
|--------|--|----------------|-------------|
| 1 | Infusion dose of 0.25 mg/kg xisomab 3G3 or placebo | 2:1 | 9-12 |
| 2 | Infusion dose of 0.5 mg/kg xisomab 3G3 or placebo | 2:1 | 9-12 |

This study includes a screening period of 28 days prior to checking-in to the clinical research unit on Day -8. From Day -7 (one week prior to dosing on Day 1) through Day -1, all patients will undergo HD 3 times and will be assessed for all scheduled procedures and endpoints before and after each HD session as per the Study Events Flow Chart ([Section 6](#)).

On Study Day 1, prior to dosing, patients will undergo baseline measurements followed by initiation of a regular HD procedure, consistently using only one type of dialyzer cartridge in each patient. Immediately after the start of blood perfusion, a single dose of xisomab 3G3 or matching placebo will be injected through a port into the flowing arterial blood in the proximal dialysis line. Patients will continue to undergo HD procedures and scheduled assessments from Day 1 through Day 12.

Study assessments will include physical examinations, vital signs, ECGs, clinical laboratory tests, HD vascular access site (AV fistula or AV graft) reaction, antibody titer (immunogenicity), AEs, PD blood sampling (coagulation parameters), and PK blood sampling to be performed throughout the study according to the Study Events Flow Chart ([Section 6](#)). On Days -7, -5, and -3 and Days 1, 3, 5, and 12, bleeding time from the HD vascular access sites on the AV fistula or AV graft (ladder or buttonhole technique) will be evaluated at the end of the HD session. The dialyzer cartridge will be rinsed and visually inspected at the end of the HD procedure and graded against a standardized visual assessment scale. After visual assessment, the used and rinsed dialyzer cartridge will be frozen and saved for later retained content (deposited blood-derived material) analysis. The number of dialyzer cartridges used for the HD session will be recorded.

Patients who withdraw prematurely from the study may be replaced at the discretion of the Investigator and Aronora, Inc. to ensure that up to 24 patients (9 to 12 patients per cohort) complete the study.

10.1.1 Confinement and Follow-Up

Patients will be housed on Day -8, at the time indicated by the CRU, until after completion of study procedures on Day 6 as indicated in the Study Events Flow Chart ([Section 6](#)). Patients will return to the CRU as per the Study Events Flow Chart ([Section 6](#)) for additional HD sessions and study procedures. At all times, a patient may be required to remain at the CRU for longer at the discretion of the Principal Investigator (PI) or designee.

All patients who received the study drug or placebo (including patients who terminate the study early) will undergo follow-up procedures at the CRU approximately 12 days after dosing.

